#### 5.3.3. Safety endpoints

Device-related adverse events (AEs), serious adverse events (SAEs), and device malfunctions by overall occurrence and imaging modality (DBT and FFDM) that occur during the study will be collected. No other clinical safety assessments will be performed.

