### 8.2. Digital Breast Tomosynthesis (DBT) and Full Field Digital Mammography (FFDM) Examinations

Prior screening DBT and screening/diagnostic FFDM images will be collected from each subject's medical record. If prior screening and/or diagnostic images/views are not available or were not collected with GE equipment, a subject will undergo study-specific DBT and/or FFDM imaging, as needed. Study-specific imaging may include bilateral 2-view (CC/MLO) FFDM and/or DBT (as needed) performed using GE systems available at the site and according to the site's standard procedures.

Two-view DBT and two-view FFDM image acquisition (both CC and MLO views) on GE equipment shall be performed within 30 days of each other, regardless if FFDM or DBT was performed before or after the patient agreed to participate in the study. Subjects requiring study-specific imaging will undergo the following procedures:

- Enter a changing room to prepare for their mammogram;
- Each subject of child-bearing potential shall wear a lead apron or have equivalent shielding during the DBT and/or FFDM procedures;
- Undergo DBT and/or FFDM procedure(s);
- Will be monitored for AEs and SAEs from study-specific DBT and FFDM and will be recorded in the source document and CRF. Device malfunctions shall be sent to the Sponsor as per Section 12.5 Management of Device Complaints.

All scanning should be performed within the standard range of scan parameters, as per the manufacturer-provided operator's manual(s) for GE FFDM and DBT devices. The scan operator should conduct DBT and FFDM exams according to the standard clinical practice at the site with consideration for:

- Subjects with large breasts, because perspiration under the breast can cause the skin to soften, and become paper-thin;
- Any existing condition that may cause unusual discomfort or tearing of the skin, which could include telling the subject the importance of correct positioning. The subject should be positioned carefully to avoid any discomfort to abnormalities such as warts, scarring, or skin which is not intact;
- Warmth of the breast support surface, which can be warm to the touch, as it contains electronic components that generate heat;
- Positioning the breast properly in FFDM and DBT in the CC position, where it is essential that the breast is lifted away from the chest wall and gently pulled forward, in order to visualize the maximum amount of breast tissue.

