#### **10.1.4. Adverse Events**

Adverse events will be reported from the time the subject enters the imaging suite for study procedures until the time the subject leaves the imaging suite after the study procedure. Device-related AEs and SAEs reported by subjects within 30 days of imaging (only those reported by subjects will be considered, and no separate 30-day follow-up is planned), and device malfunctions occurring in the safety population will be summarized with subject counts overall and by modality (DBT and FFDM). Additionally, individual subject listings will be provided to detail all AE/SAE information collected.

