## 12.3. Management of Adverse Event Reporting

Any adverse events will be recorded in the subjects study record and the Adverse Event Case Report Form. The following information should be obtained:

- Description of Event

- Date of onset and resolution
- Intensity (mild, moderate, severe)
  - **Mild:** Symptom(s) barely noticeable to the subject or does not make the subject uncomfortable. The AE does not influence performance or functioning. Prescription drugs are not ordinarily needed for relief of symptom(s).
  - **Moderate:** Symptom(s) of a sufficient severity to make the subject uncomfortable. Performance of daily activities is influenced. Treatment of symptom(s) may be needed.
  - **Severe:** Symptom(s) of a sufficient severity to cause the subject severe discomfort. Treatment for symptom(s) may be given.
- Serious (yes/no)
- Relationship to device (unrelated, possibly related, probably related)
  - **Unrelated:** The adverse event is reasonably expected to be related to (or caused by) a concurrent illness, effect of another device/drug or other cause, and is unlikely related to the investigational product
  - **Possibly related:** The adverse event is reasonably expected to be related to the investigational product, and an alternative etiology is equally or less likely compared to the potential relationship to investigational product
  - **Probably related:** There is a strong relationship to investigational product, or recurs on re-challenge, and another etiology is unlikely, or there is no other reasonable medical explanation for the event.
- Treatment given and/or action taken (procedure stopped, withdrawn from study, no action)
- Anticipated (yes/no)

Adverse events will be reported to the local EC/IRB per their policy.

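### Can device events be counted by modality when the 30-day periods after DBT and FFDM overlap and no assignment rule is written?

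*Combined protocol and SAP*

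**What the plan says.** Section 5.3.3 sets the safety endpoint: device-related AEs, SAEs and "device malfunctions by overall occurrence and imaging modality (DBT and FFDM) that occur during the study will be collected". The Synopsis repeats it.

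Section 10.1.4 has two parts. The first reports adverse events "from the time the subject enters the imaging suite for study procedures until the time the subject leaves the imaging suite". The second takes "Device-related AEs and SAEs reported by subjects within 30 days of imaging", with no separate follow-up contact, and adds malfunctions of the device. Of all these it says that those "occurring in the safety population will be summarized with subject counts overall and by modality (DBT and FFDM". Individual listings are added.

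Section 8.2 requires that the two-view DBT and FFDM "image acquisition (both CC and MLO views) on GE equipment shall be performed within 30 days of each other". By the same section, this limit holds "regardless if FFDM or DBT was performed before or after the patient agreed to participate in the study". For women who need study-specific imaging it adds: "Will be monitored for AEs and SAEs from study-specific DBT and FFDM". Table 1 in Section 8 marks safety assessments under Study Imaging only.

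The AE items in Section 12.3 are description, onset and resolution dates, intensity, seriousness, "Relationship to device (unrelated, possibly related, probably related", action taken, and whether the event was anticipated.

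**The concern.** Three features together suggest that the by-modality counts cannot be reproduced.

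- **Overlap.** Both limits are 30 days, so for any gap shorter than 30 days some calendar days fall after both exams and inside both reporting periods.
- **No tie-break in the listed items.** Section 12.3 names neither the modality nor the preceding exam, and grades relationship to a single device. Section 4.3 records device identifiers, but Section 3.1 describes DBT as an add-on to the FFDM platform, so an identifier need not separate the two. Section 12.1 knows of no DBT effects beyond those of mammography, so the kind of event does not separate them either.
- **Scope.** Sections 8 and 8.2 speak of study imaging, whereas the 30-day clause in Section 10.1.4 says only *imaging*. GE images may predate consent, and the Safety Population is everyone enrolled (Sections 10.1.2 and 7.4). An event after a clinical GE exam done before consent might be counted or not.

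If this held in full, two analysts could produce different DBT and FFDM counts, and even different overall counts, from the same events. The endpoint is a planned one, and Section 15.1 says the image data are meant for a regulatory submission.

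**Working it through.** The plan gives no figure to reproduce: it states no expected number of events and no distribution of gaps between exams.

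**Step 1: overlap in calendar time.** Inputs: a 30-day reporting limit (Section 10.1.4) and a gap g between exams of 0 to 30 days (Section 8.2). With the first exam on day 0 and the second on day g, the periods are [0, 30] and [g, g + 30]. Overlap = 30 − g days; share of one period = (30 − g)/30.

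| Gap g (days) | Overlap (days) | Share of one period |
|---|---|---|
| 0 | 30 | 100% |
| 7 | 23 | 77% |
| 14 | 16 | 53% |
| 21 | 9 | 30% |
| 30 | 0 | 0% |

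**Step 2: the largest possible effect on counts.** Let k women have an event in the overlap and count each under at least one modality. DBT and FFDM can then each be 0 to k, with a sum from k to 2k, against an overall count of k. For an assumed k = 4 there are 5 × 5 = 25 pairs. Those with a sum below 4 number 1 + 2 + 3 + 4 = 10, which leaves 15 possible results. For k = 1 the sum is 1 to 2; for k = 10 it is 10 to 20; for k = 0 nothing changes.

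**Step 3: why Step 2 is a ceiling.** It needs analysts to disregard everything recorded about the event.

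- The 30 days says which subject reports are considered. It does not say that an event belongs to every exam in the preceding 30 days. The shares in Step 1 are therefore shares of calendar time, not of ambiguous events.
- Section 12.3 records onset date, description, relationship and action taken, including whether a procedure was stopped. The effects named in Section 12.1 are bruising, discomfort and skin injury. When the exams are on different days, onset will often point to one of them.
- Malfunctions carry no 30-day period, and events in the suite at a visit with one modality can usually be placed from context.
- A sum above k is not in itself an error. In a within-subject design a woman may properly appear under both modalities.

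**Step 4: which women are affected.** Reading the first part of Section 10.1.4 with Table 1 and Section 8.2, the imaging that counts is study imaging. Section 5.3.3 also confines events to the study, and Section 6.2 starts participation at enrollment.

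| Imaging history | Modality open to an event, study-imaging reading |
|---|---|
| Both GE exams before enrollment | Not counted |
| DBT before, FFDM as study imaging | FFDM only |
| FFDM before, DBT as study imaging | DBT only |
| Both as study imaging | DBT or FFDM |

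Only the last row is ambiguous. By Table 1, note c, repeat imaging is done only where suitable earlier two-view images are lacking or were not made on a GE system. The protocol gives no number for this group. Under the looser reading, which takes *imaging* apart from the sentence before it, all four rows could be ambiguous.

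**Step 5: is modality recorded?** Section 12.3 lists none, but Section 5.3.3 and the Synopsis say that events by modality will be collected. The list in Section 12.3 is not stated to be complete, and the case report form is not part of the document. A missing field cannot be shown.

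**The case for a change.** The strongest case for a change is that a planned endpoint has no assignment rule, while a rule would cost a few sentences. A modality field on the form would not settle an event noticed at home after a visit with both exams. Section 12.1 expressly provides for women who need both exams repeated, so the ambiguous group is foreseen. With few events, each assignment visibly moves the table. The scope wording could also reach the overall count: a woman with a clinical GE DBT who then consents and reports bruising on day 10 fits the 30-day clause but not Section 8.2.

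Part of this stands. No sentence covers a device-related event after both exams at one visit, and the word *imaging* in Section 10.1.4 is looser than the wording of Section 8.2. What does not stand is that the counts as a whole are undetermined. The day-10 example depends on separating the 30-day clause from the study-procedure sentence before it and from Table 1. Splits such as 4/0 or 0/4 for four unassignable events would need an arbitrary choice that no careful analyst would make without saying so.

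**Conclusion.** The observation is accurate but amounts to a gap in detail, and the plan does not need to change. The open case is a device-related event reported after both modalities were done as study imaging, chiefly at one visit or a few days apart. An analyst would count it once overall and show it as not separable between the exams, or under both with a note. Section 10.1.4 already provides listings of all AE information collected, so a reader can recount any such event.

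Nothing else turns on the result. Section 5.1 states no hypothesis, Section 10.1.1 limits the study to a descriptive summary, and Section 10.4 sets no statistical success criterion. The planned quantities are counts, so no denominator is in dispute.

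The numerical effect is at most 0 to k for each modality, where k is the number of women with a truly unassignable event; k is unknown and may be zero. The conclusion rests on two assumptions: that modality is collected, as Section 5.3.3 says it will be, and that Section 10.1.4 is read together with Section 8.2 and Table 1. If the form proved to hold no modality information, more events would fall into the not-separable group. The by-modality counts would then be less informative, but the listings and the overall count would be unaffected.

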#### **10.1.5. Methods**

All descriptive analyses will be performed using SAS V9 (SAS Institute, Inc. Cary, North Carolina, USA).

Any deviations, changes, or additions to the statistical analysis outlined in the protocol will be described with reasons for the deviations in the final Clinical Study Report.

### **10.2. Interim Analysis**

No interim analysis is prospectively planned. The Sponsor may, however, review and monitor data collected to date at any point during the study for purposes of monitoring study conduct and completion.

### **10.3. Handling of Missing Data**

There will be no imputation of missing data and collected data will be analyzed as is.

### **10.4. Pass/Fail Criteria of the Study**

No statistical criteria for success are defined for this accrual study, which will be considered successful if subject number and truth accrual targets are met, without consideration for subsequent analysis results.

## 11. DEVIATIONS

### 11.1. Management of Protocol Deviations

Deviations to the protocol may occur when necessary to protect the life or physical well-being of a subject. Except in an emergency, prior approval by the Sponsor is required for changes in, or planned deviations from this protocol. If these changes affect the scientific soundness or the safety and welfare of the subject, prior ethics committee/institutional review board (EC/IRB) approval is also required. Planned Protocol Deviation documentation must be filed in the Site Study Regulatory Binder. There are two types of unplanned protocol deviations, critical deviations and non-critical deviations. All deviations must be documented and reported, the criticality of the deviation will determine the reporting path.

#### Critical Deviations:

Critical protocol deviations are those that significantly affect the safety, efficacy, integrity or conduct of the study. These deviations must be reported to the Sponsor no later than 5 working days from awareness of occurrence and reported to the EC per the deviation reporting policy.

If an Investigator uses a device without obtaining informed consent, per Section 14.4 Informed Consent and Privacy Requirements, the Investigator shall consider this a critical deviation and report the event to the Sponsor and the EC/IRB within 5 working days of the occurrence.

#### Non-critical Deviations:

Non-critical protocol deviations are those that DO NOT significantly affect the safety, efficacy, integrity or conduct of the trial. These deviations must be documented on the Case Report Form Protocol Deviation page and will be reviewed by the study monitor.

## 12. COMPLAINT HANDLING AND ADVERSE EVENT REPORTING

### 12.1. Foreseeable Adverse Events and Device Effects

There are no known additional medical risks or side effects from DBT beyond those of conventional mammography. Expected AEs that apply to mammography and are also applicable to digital mammography using the Senographe Essential system may include but are not limited to:

- bruising;
- discomfort;
- skin irritation, abrasions, bruising or tears.

There is also the risk that imaging studies will falsely indicate an abnormality that could cause extra procedures to be done, and cause unnecessary anxiety for subjects.

The breast radiation dose from a two-view DBT acquisition is approximately the same as from conventional two-view FFDM mammography. In this study, subjects must have undergone

FFDM and DBT on GE equipment. If they have not, they must have FFDM CC and MLO views as well as DBT CC and MLO repeated on GE equipment, as applicable.

Patients will thus get up to four-times (if repeat DBT and FFDM imaging is required) the radiation dose that they normally would if they underwent mammography outside of the clinical trial, a dose within expected limits for routine mammography procedures and considered ALARP to complete this study.

It is generally agreed that the risk to a fetus due to radiation from screening mammography is extremely low; however, clinical practice is to try to determine pregnancy status of women referred for mammography and to not allow women known or suspected to be pregnant to undergo screening mammography or other elective radiologic procedures.

## 12.2. Adverse Event Definitions

**Adverse Event (AE):** As defined by EN ISO 14155-2011: any untoward medical occurrence, unintended disease or injury, or untoward clinical signs (including abnormal laboratory findings) in subjects, users or other persons, whether or not related to the investigational medical device.

**Serious Adverse Event (SAE):** As defined by EN ISO 14155 – 2011: an adverse event that

- (a) led to death;
- (b) led to a serious deterioration in the health of the subject, that either resulted in:
  - (1) a life-threatening illness or injury, or
  - (2) a permanent impairment of a body structure or a body function, or
  - (3) in-patient or prolonged hospitalization, or
  - (4) medical or surgical intervention to prevent life-threatening illness or injury or permanent impairment to body structure or a body function;
- (c) led to fetal distress, fetal death or a congenital abnormality or birth defect.

**Anticipated:** Any adverse event and/or reaction, the specificity or severity of which is consistent with the EC/IRB approved informed consent, protocol, investigator brochure, or product labeling.

**Unanticipated Adverse Device Effect (UADE)** : As defined by 21 CFR 812.3: means any serious adverse effect on health or safety or any life-threatening problem or death caused by, or associated with, a device, if that effect, problem, or death was not previously identified in nature, severity, or degree of incidence in the investigational plan or application (including a supplementary plan or application), or any other unanticipated serious problem associated with a device that relates to the rights, safety, or welfare of subjects.

## 12.3. Management of Adverse Event Reporting

Any adverse events will be recorded in the subjects study record and the Adverse Event Case Report Form. The following information should be obtained:

- Description of Event

- Date of onset and resolution
- Intensity (mild, moderate, severe)
  - **Mild:** Symptom(s) barely noticeable to the subject or does not make the subject uncomfortable. The AE does not influence performance or functioning. Prescription drugs are not ordinarily needed for relief of symptom(s).
  - **Moderate:** Symptom(s) of a sufficient severity to make the subject uncomfortable. Performance of daily activities is influenced. Treatment of symptom(s) may be needed.
  - **Severe:** Symptom(s) of a sufficient severity to cause the subject severe discomfort. Treatment for symptom(s) may be given.
- Serious (yes/no)
- Relationship to device (unrelated, possibly related, probably related)
  - **Unrelated:** The adverse event is reasonably expected to be related to (or caused by) a concurrent illness, effect of another device/drug or other cause, and is unlikely related to the investigational product
  - **Possibly related:** The adverse event is reasonably expected to be related to the investigational product, and an alternative etiology is equally or less likely compared to the potential relationship to investigational product
  - **Probably related:** There is a strong relationship to investigational product, or recurs on re-challenge, and another etiology is unlikely, or there is no other reasonable medical explanation for the event.
- Treatment given and/or action taken (procedure stopped, withdrawn from study, no action)
- Anticipated (yes/no)

Adverse events will be reported to the local EC/IRB per their policy.

## **12.4. Management of Serious Adverse Event and Unanticipated Adverse Device Effect Reporting**

All SAEs and or UADEs will be documented as above and reported in writing to the Sponsor within 72 hours of knowledge of the event. The Investigator shall submit the Adverse Event Case Report Form and GEHC\_GQP\_10.07.005\_F002 Site Notification and Assessment of Serious and Unexpected Adverse Events (DOC0910335) with redacted supporting documentation to SAE mailbox.

If the event resulted in the death of a subject, the event shall also be reported via telephone to the Sponsor within 24 hours of knowledge of the event. SAEs will be reported to the local EC/IRB per their policy.

## **12.5. Management of Device Complaints**

Any complaints regarding the operation of the device or software or any malfunctions are to be reported to the Clinical Affair Project Manager.

## **13. EARLY TERMINATION OR SUSPENSION**

### **13.1. Criteria for Early Termination or Suspension**

There are no formal termination criteria for this study. The Sponsor reserves the right to terminate the study at any time. Investigators have the responsibility to comply with International Conference on Harmonisation (ICH) E6-Good Clinical Practice (GCP) guidance. The Sponsor, the Institutional/Independent Review Board (IRB) or Ethics Committee (EC), or the health authorities may terminate a center for the following (but not limited to) reasons:

1. If any SAEs or other technical safety issues occur;
2. Failure of the investigator to comply with pertinent ICH E6-GCP guidelines and regulations;
3. If serious protocol violations occur;
4. Submission of knowingly false information from the research facility to the Sponsor, clinical monitor, or other party involved in the study;
5. Failure of the investigator to enroll subjects into the study at an acceptable rate as agreed to with the Sponsor;
6. Repeated failure to have imaging data transferred or CRF completed and ready for submission to the Sponsor in the agreed time frame.
7. If the Sponsor determines that unanticipated adverse event(s) presents an unreasonable risk to subjects or for any other reason as Sponsor determines to be appropriate.

The Sponsor will promptly notify the Investigators of any determination to terminate the study outside of the protocol timeframe.

Termination shall occur no later than 5 working days after the Sponsor makes the determination and no later than 15 working days after Sponsor first received notice of the effect.

The Sponsor will provide each Investigator with written guidelines/instructions on termination processes and timelines.

The Investigator is responsible for reporting the early termination to their local EC/IRB.

